preferences in the videos. Including individuals with mild to moderate cognitive limitations in advance care planning discussions and expressing their EOL preferences is warranted, viable and an ethical approach.^{13,14} Incorporating Me & My Wishes into the care planning process is expected to provide an efficient and effective way for residents to communicate their care preferences for today and at EOL, and to positively influence confidence in communicating preferences and in facilitating documentation of care planning documents.

Our long-term goal is to scale and fully incorporate Me & My Wishes into multiple settings providing long term services and supports. Ultimately, integrating Me & My Wishes videos into the electronic health record or another platform allows for video viewing by multiple individuals and disciplines in various settings. Our short-term goal, and the goal of this proposal, is to conduct Stage II efficacy testing of Me & My Wishes. We will employ a randomized wait-list control design of six nursing homes (48-54 residents). Three nursing homes will be assigned to an early intervention group (residents will share videos initially) and three assigned to the wait-list controls (residents will delay sharing videos). Videos can be viewed two ways: 1) in resident quarterly care conferences; and 2) via a secured web-based link for resident-identified family members. After video viewing, the resident, family and staff can discuss key messages and preferences of the video and add to the care plan.

Specific Aim 1: Examine the efficacy of the Me & My Wishes intervention among a sample of nursing home residents with dementia.

Hypothesis 1: Compared to the waitlist control group (Group 2), the intervention group (Group 1) will have an increase in the proportion of residents with documented goals of care discussions or self-reported conversations about preferences 90 days post video viewing.

Specific Aim 2: Examine self-efficacy of communicating preferences among residents with dementia, informal (family) and formal (staff) caregivers.

Hypothesis 2: Compared to the waitlist control group (Group 2), the intervention group (Group 1) will have greater self-efficacy scores for communicating preferences 90 days post video viewing.

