 - Conversations are not often passed on to others or recorded.
 - Preferences for care today and at the end-of-life can be a difficult topic to discuss.
 - When they do occur, conversations often happen too late or at times of crisis or transition such as hospitalization.
 - Advance Care Planning (ACP) is associated with higher quality of life and satisfaction with care.
 - ACP is also associated with decreased rates of depression and anxiety among bereaved loved ones.
 - Lack of ACP often results in more invasive care than is desired.
- Reviewing the consent forms and obtaining consent from those who wish to participate.
- Scheduling the date video recording will take place and informing NH staff, as well as other scheduling.
- Performance of the Chart Review and completion of the Demographic and Medical Record Review Forms as described later in this chapter.

Staff, Family and Resident Recruitment

Staff Consent

- ❖ Care Conference Staff
Care Conference Team Consent Letter (Appendix F)

Care Conference Staff Consent

Recruitment of staff members will occur in person. The care conference team members of the resident will receive a recruitment letter and staff caregiver consent either in person or via email stating the purpose of the study or at a staff meeting or care conference prior to video sharing. The SC will explain the study, review the IRB-approved informed consent document, and answer any questions the care conference team member might have. Ample time will be provided for the staff member to consider participation. A follow-up visit can be readily scheduled by the SC. For staff members who agree to participate, we will document affirmation of consent. Potential interdisciplinary care team participating in care conference will be nurse manager, social services director, dietary manager, nurse's aide

Strategies for Communicating Research to Staff Members.

Information session in standup meeting

Attend Resident Council Meeting

Attend All-Staff meeting

Approach staff members 1:1 on scheduled time

- May include positive testimonials if applicable

Me and My Wishes: Study Stand-Up Checklist

- NH Champion preferred day/time to meet weekly/bi-weekly (obtain more than one date since we will be juggling a few facilities).
- NH champion's preferred introduction schedule. Do they prefer to introduce SC's to residents all at same time or separately after each consent?

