- The hard copy will be kept in a locked cabinet and will be transferred to RedCap which is password protected and in an encrypted computer
- Only PI, co-investigators and research team will have access to the extracted data
- The de-identified extracted data will be stored in a locked cabinet at the College of Nursing.

List of data/information to be extracted from the resident chart:

- Age
- Gender
- Education
- Pay source
- Marital status
- Insurance
- Diagnoses
- Mood
- Level of care
- Length of stay
- Presence of documents such as Advance Directives, POLST, or Code Status
- Presence of goals of care conversations (may be found in nursing/social services notes). Document location of where found on form (facilities may differ on where this type of information is located).

Tips where to look for the data in the EHR:

- Demographic form
- Kardex
- Care plan
- Face-sheet
- MDS
- Documents
- *Refer to FAQ for more tips

Frequently Asked Questions (FAQ) during data extraction time:

1. I cannot find information about education anywhere in the chart?

This is common. You can ask the resident after video recording.

2. I found the racial background information but not the ethical background on the chart?

You can ask the resident about her or his ethnic background before video recording begins.

3. What is the difference between 'pay source' and 'Insurance'?

The demographic and clinical form gives you option about what to fill out. Most NH residents have Medicaid and/or Medicare. But you will need to find that information in the chart. And then you will need to see if the resident also have other private insurance (e.g. Elderplace or a type of Medicare Advantage).

4. The resident has a list of diagnoses (old and current) and I'm not sure if I need to write each one of them on the form?

Include at least 10 diagnoses on the form. If available, you can ask a clinician which are most relevant. You may have to make a judgment call about which DXs to include.

5. I found several admission dates on the chart; which ones do I write on the form?

We will collect the initial admission date and the *most recent* admission date, look at the chart carefully and make sure you have the correct dates. If the original date and most recent date is the same, enter the same date for both.

6. Do I count the length of stay from the most recent admission date?

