We track two admission dates (initial admission date and most recent admission date). Please calculate length of stay from both these dates.

7. What is the best way to find the Advance Directive information?

This depends. Some charts have this information on the demographic tab and Documents tab and some only have this information on the POLST form. You will need to look carefully in multiple places. POLST may be a separate document on its own. Once you find the form, you will need to look at it carefully to find the rest of the information.

8. I found the care plan but I'm not sure if the goals for the care are consistent with resident preferences.

You may or may not find evidence of resident preferences written on the care plan. Review the care plan carefully and look for any evidence that is consistent with the resident preferences such as resident statements – this may be written in quotes.

9. Could there be any other place where the resident preferences is documented?
Yes. There may be a standardized document that has the resident preferences. If the facility has such as form, you will need to include the source and location of information.

10. When I do a 90-day follow-up data extraction on the same chart, how do I get access to the chart and what is the procedure?
You will need to notify the NH administrator ahead of time about your intent and when you will be at the facility. Other than that, you will follow the same procedure outlined on the data extraction protocol for initial Demographic and Medical Record Review Forms.

Participant Confidentiality

Participant identification (ID) numbers will be assigned for all individuals approached to track those who enroll and those who decline. Study sites will be randomly assigned to an intervention or wait-list control group. Use the REDCap database to track all individuals (even though who decline). This number will be used instead of the participant's name on all forms and tracking. Write the participant ID on the top right hand corner of all documents except for the consent forms.

Data Security

- ❖ Documents
Consent forms are stored separately from all other recruitment and enrollment documents, including surveys where appropriate.
- ❖ Audio Recordings
Audio recordings are to be uploaded to the appropriate folder on UBox, then deleted from the audio recorder. Audio recordings are deleted once transcription has been completed, compared to audio recording, and finalized.

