**National Clinical Trial (NCT) Identified Number: NCT03861429**

**Principal Investigator: [name] NHA**

**Sponsor: University of Utah**

**Grant Number: R21AG058094**

**Funded by: NIA**

**Statistical Analysis Plan**

**August, 1, 2019**

## Randomization

We will employ a randomized wait-list control design with nursing homes and assisted living facilities. We block randomized five nursing homes and three assisted living communities in the Pacific Northwest into two groups based on size, proportion of residents with Medicaid, and proportion of residents with mild to moderate cognitive impairment. In Group 1 (early intervention group) NHs, videorecording, editing, and viewing will occur within three months of baseline. In Group 2 (delayed sharing) NHs, residents will be on a wait-list; after the delayed start, their video will be produced and viewed within three months.

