## Primary & Secondary Outcomes

We will calculate summary statistics for baseline demographics by intervention group, to assess comparability of groups and validate randomization scheme. We will use mixed modeling to compare the outcome measures goals of care discussions and self-efficacy of communicating preferences between Group 1 (early intervention) and Group 2 (wait-list) at 3 time points. Our specific model will be:  $Y = B_0 + B_1X + B_2T + B_3(X \cdot T) + e$  where, Y= goals of care discussions or self-efficacy of communicating preferences, X = Treatment condition (Group 1 vs. Group 2), T = Time point (baseline, 3 months, 6 months). Evaluation of the fixed effect of Treatment condition will tell us whether the two groups differ on average across all time points. The fixed effect of Time will tell us whether goals of care discussions change over time. Evaluation of the interaction of Treatment by Time will tell us if the groups change differentially, and will be the effect of primary interest.

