## Goals of Care

We analyzed results with an intent to treat approach using SPSS Version 24.0 (SPSS, Armonk, NY). Multilevel logistic regression (generalized estimating equations [GEE] with an autoregressive (1) working correlation matrix, logit link function) were fitted to assess the primary hypotheses. The models account for the repeated measures (3 or 4 time points), correlated, data structure per person. An additive model was conducted with contrast coding for each time point, treatment, and follow-up effects.

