### **Concordance Analysis**

Analyses were conducted using SPSS Version 24.0 (SPSS, Armonk, NY) using an intent to treat approach. Multilevel linear regressions (generalized estimating equations [GEE] with an autoregressive (1) working correlation matrix) were fitted to assess concordance of preferences between the resident videos and staff and family surveys at three (intervention group) or four (wait-list control group) time points. The models account for the repeated measures (three or four time points), correlated, data structure per person. Because this study used a waitlist control design, data includes the initial baseline data for both groups and second baseline data for the waitlist group. An additive model was conducted with contrast coding for each time point, treatment, and follow-up effects. This allowed us to compare the groups by the different times they received the video, with Time 1 (Baseline) as the reference category. For example, a participant in the Immediate group at time of video sharing would receive contrast coding: Time 2 (1); Time 3 (0), Time 4 (0), Treatment (1), Follow-up (0). While a participant in the Wait-list (Control) group at time of video sharing would receive contrast coding: Time 2 (0), Time 3 (1), Time 4 (0), Treatment (1), Follow-up (0). We stratified our analysis by the three different types of participants - residents, family members, and staff members.

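### Whole facilities are randomized, but the GEE models for the primary hypotheses treat each person as independent; if outcomes correlate within facility, the false-positive rate exceeds 5%

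*SAP*

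**What the plan says.** **Unit of randomization.** The SAP, Randomization, states: "We block randomized five nursing homes and three assisted living communities in the Pacific Northwest into two groups". The protocol, Stage II Efficacy, has six nursing homes and 48–54 residents: "Three nursing homes will be assigned to an early intervention group", and the other three form the wait-list. Under Participant Confidentiality it adds: "Study sites will be randomly assigned to an intervention or wait-list control group".

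**Unit of analysis.** The SAP, Goals of Care, fits a logistic GEE with an AR(1) working correlation to test the primary hypotheses, and says: "The models account for the repeated measures (3 or 4 time points), correlated, data structure per person". The Concordance Analysis section repeats this for a linear GEE: "The models account for the repeated measures (three or four time points), correlated, data structure per person". Both describe an additive model with contrasts for time, treatment and follow-up. The worked coding under Concordance Analysis lists Time 2, Time 3, Time 4, Treatment and Follow-up, with no arm term.

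**Other model.** Primary & Secondary Outcomes describes a mixed model with treatment, time and their product: "Evaluation of the interaction of Treatment by Time will tell us if the groups change differentially, and will be the effect of primary interest". It names no facility effect, though it does not exclude one.

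**Sample size.** Power and Sample Size gives f = .213 for 48 residents, three time points, correlation .5, power .90 and alpha .05, with no ICC or design effect.

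**The concern.** Treatment is assigned to 8 (or 6) units but tested as if about 48 residents were independent. Chance differences among a few facilities can then be reported as an effect of the videos, in the very models the SAP names for the primary hypotheses.

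The documents make facility-level correlation plausible without measuring it. On goals-of-care notes, the protocol's Chart Review section warns that "facilities may differ on where this type of information is located", and documented goals-of-care discussions are part of the Hypothesis 1 outcome. Residents of one facility are also likely to share a care-conference team: "Potential interdisciplinary care team participating in care conference will be nurse manager, social services director, dietary manager". The SAP mixes nursing homes with assisted living communities as well.

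**Working it through.** **1. The plan's own figure.** For a within-between interaction, λ = f²·N·m/(1 − ρ). With f = .213, N = 48, m = 3 and ρ = .5, λ = .0454 × 48 × 3/.5 = 13.07. With df1 = (2 − 1)(3 − 1) = 2 and df2 = (48 − 2)(3 − 1) = 92, power is .8998. So f = .213 reproduces, with residents taken as independent.

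**2. Detectable effect with facility as the unit.** Assume 48/8 = 6 residents per facility and a within-facility correlation r of changes. The design effect is DE = 1 + (6 − 1)r, effective N is 48/DE, and facility-level df2 = (8 − 2) × 2 = 12.

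| r (assumed) | DE | N/DE | Power at f = .213, df 92 | f for 90%, df 92 | Power at f = .213, df 12 | f for 90%, df 12 |
|---|---|---|---|---|---|---|
| 0 | 1.00 | 48.0 | 90% | .213 | 82% | .239 |
| .05 | 1.25 | 38.4 | 82% | .238 | 72% | .267 |
| .10 | 1.50 | 32.0 | 74% | .261 | 64% | .293 |
| .20 | 2.00 | 24.0 | 61% | .301 | 51% | .338 |

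**3. Why a time-constant facility difference does not cancel in the GEE.** Use the coding shown under Concordance Analysis, the identity link and AR(1) = .5 (assumed). The GLS weights on the early group's Times 1, 2 and 3 are:

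- Treatment: (−.5, 1, 0), sum .50
- Follow-up, if Treatment returns to 0 at follow-up: (−.75, 1, 1), sum 1.25
- Follow-up, if Treatment stays 1: (−.25, 0, 1), sum .75

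The wait-list group has the opposite weights on the same times and zero on Time 4. A constant difference D between the arms' facilities therefore enters as 0.50 D, 1.25 D or 0.75 D. The SAP shows codes only at video sharing, so the Follow-up case is unknown. For AR(1) from .2 to .8 the sums run from .80 to .20 (Treatment), and from 1.76 to .56 or .96 to .36 (Follow-up).

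**4. False-positive rate of the logistic GEE with person-level sandwich variance.** Assumptions: no true effect, 40% base rate, AR(1) .5, latent-scale ICC, equal allocation, blocking not modelled. There were 6,000 runs per setting for 8 × 6 (simulation SE 0.3–0.4 points) and 4,000 for 6 × 8.

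| Term, facilities × residents | Treatment code at follow-up | ICC 0 | .05 | .10 | .20 |
|---|---|---|---|---|---|
| Follow-up, 8 × 6 | 0 | 5.1% | 7.6% | 9.9% | 13.0% |
| Follow-up, 8 × 6 | 1 | 5.1% | 6.3% | 8.1% | 10.8% |
| Treatment, 8 × 6 | 0 | 4.7% | 5.7% | 7.4% | 8.8% |
| Treatment, 8 × 6 | 1 | 4.9% | 6.2% | 7.5% | 9.5% |
| Follow-up, 6 × 8 | 0 | 5.6% | 8.2% | 10.5% | 16.0% |
| Follow-up, 6 × 8 | 1 | 5.0% | 6.9% | 9.0% | 14.3% |

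A separately coded simulation (1,200 runs per setting) gave 4.8–5.4% with no facility correlation. At latent ICCs of .05, .10 and .20 (about .03, .06 and .13 on the observed scale) it gave 6.0–8.6%, 6.7–9.3% and 8.2–12.8% for 8 facilities; these ranges include settings with facility-by-time variance.

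The linear concordance GEE at 8 × 6 gave, for Follow-up, 6.8% at ICC 0 and then 8.6/10.4/13.0% (code 0), or 5.9% and then 8.0/9.9/12.9% (code 1). Its excess at ICC 0 comes from having few persons.

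**5. The Treatment × Time model.** Here a constant facility difference cancels: 4.8–5.2% at every constant ICC (20,000 runs). Facility-by-time variance does not cancel. At 5% of total variance the rate is 9.0–10.6% per contrast (12.6% joint test), and at 10% it is 12.6–15.9% (19.8% joint).

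**The case against.** The SAP calls the models multilevel, blocks facilities on size, Medicaid share and cognitive impairment, and plans a propensity score. None of this fills the gap. The SAP explains the multilevel model as a GEE with per-person correlation. Blocking may reduce imbalance but does not enter the GEE variance. The propensity score uses participant characteristics.

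The stronger objections concern size, and several stand:

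- No ICC is given, and at ICC .05 with eight facilities the inflation is modest (5.7–7.6%). Unmodelled blocking could lower it further. The 40% base rate was not varied.
- Part of the power loss is the price of facility-level degrees of freedom: at zero correlation power already falls from 90% to 82%. Also, f = .213 refers to the interaction, where only facility-by-time variance matters, and the documents say nothing about its size.
- The multipliers of D hold on the linear scale and depend on AR(1). For the logistic model they are approximate.
- The explicit coding appears only under Concordance Analysis. Applying it to Goals of Care is an inference, though the two sections describe the additive model in the same words.
- The protocol's remarks on record location and care teams make facility correlation plausible; they do not show that outcome rates differ.
- Concordance serves a descriptive aim, so false positives matter less there.

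These points qualify the magnitude. They do not supply the missing facility-level variance.

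**Conclusion.** The concern holds and must be fixed. Facilities are randomized, and the stated primary analysis allows for correlation only within person. With any positive facility correlation the p-values are too small; that direction does not depend on the assumed values. For latent ICCs of .05 to .20, the error rate is about 6–13% with eight facilities. With the protocol's six homes, the Follow-up term reaches 14–16% at ICC .20. The Treatment × Time model is exposed only to facility-by-time variance. Confidence is high in the omission and lower in the exact size.

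**What to change.** Make facility the independent unit in the resident, staff and family models, by one of these routes:

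1. **GEE clustered on facility, with a small-sample-corrected sandwich and a t reference** on 8 − 2 = 6 df (4 df with six homes). Merely naming facility as the GEE subject is not enough: the uncorrected sandwich gave 12–16% false positives at every ICC, including 0. The Kauermann-Carroll correction with t(6) gave 3.8–6.0% in all settings, including facility-by-time variance. Mancl-DeRouen with t(6) gave 2.0–3.4% for constant facility ICC, which is conservative.
2. **A mixed model with facility, facility-by-time and person random effects**, and Kenward-Roger or Satterthwaite df. This was not simulated. A facility intercept alone is not enough, because it leaves facility-by-time variance in the error.
3. **As a simple check, a t test on the 8 facility mean changes (6 df)**, which gave 4.7–5.3% in all settings run. Name the contrast. Under the SAP's coding, Time 2 − Time 1 estimates Treatment. Time 3 − Time 1 estimates Follow-up if Treatment stays 1, but Follow-up minus Treatment if it returns to 0. In the latter case the sum of the two changes estimates Follow-up.

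A facility-level permutation test must respect the blocks. Eight facilities split 4:4 without restriction give 70 allocations and a minimum two-sided p of 2/70 = .029; four matched pairs give 16 and 2/16 = .125.

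The SAP should also state the block structure, the arm split and the Treatment code at follow-up, write out the facility and facility-by-time terms in the Treatment × Time model, and reconcile six homes with eight facilities. The detectable effect should be restated with an assumed ICC and facility-level df.

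The cost is SAP wording and re-analysis of data already held. If the named software lacks a corrected sandwich, route 3 needs only eight facility means per contrast. Intervals will be wider and the detectable effect less favourable than f = .213.

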### **Concordance Analysis**

Analyses were conducted using SPSS Version 24.0 (SPSS, Armonk, NY) using an intent to treat approach. Multilevel linear regressions (generalized estimating equations [GEE] with an autoregressive (1) working correlation matrix) were fitted to assess concordance of preferences between the resident videos and staff and family surveys at three (intervention group) or four (wait-list control group) time points. The models account for the repeated measures (three or four time points), correlated, data structure per person. Because this study used a waitlist control design, data includes the initial baseline data for both groups and second baseline data for the waitlist group. An additive model was conducted with contrast coding for each time point, treatment, and follow-up effects. This allowed us to compare the groups by the different times they received the video, with Time 1 (Baseline) as the reference category. For example, a participant in the Immediate group at time of video sharing would receive contrast coding: Time 2 (1); Time 3 (0), Time 4 (0), Treatment (1), Follow-up (0). While a participant in the Wait-list (Control) group at time of video sharing would receive contrast coding: Time 2 (0), Time 3 (1), Time 4 (0), Treatment (1), Follow-up (0). We stratified our analysis by the three different types of participants - residents, family members, and staff members.

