## Power and Sample Size

Sensitivity analysis was conducted with G-Power 3.1. With a proposed sample size = 48, 2 Groups, 3 timepoints, correlation between time points = .5, power = .90, and alpha = .05, we will be able to detect a medium effect size  $f = .213$  using a general linear modeling of repeated measures looking for within-between subjects' interaction. T= Time point (baseline, 3 months, 6 months).

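### H1 and H2 concern 90 days after viewing, but the SAP's deciding test is a group-by-time interaction that does not single out that visit, and no 90-day contrast is named

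*SAP*

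**What the plan says.** - **Hypotheses.** Protocol Chapter Two, Hypotheses 1 (goals of care discussions) and 2 (self-efficacy), compares Group 1 (early) with Group 2 (wait-list) 90 days after viewing. Protocol Chapter Four sets surveys at baseline, sharing and 90 days after sharing.
- **Main model.** SAP, Primary & Secondary Outcomes, covers both outcomes with group, time and their product, at baseline, 3 and 6 months. "Evaluation of the interaction of Treatment by Time will tell us if the groups change differentially, and will be the effect of primary interest". No visit is singled out, and the section does not say whether time is categorical or linear.
- **Power.** SAP, Power and Sample Size, is computed for that interaction with 48 residents, 2 groups, 3 time points and correlation .5: "power = .90, and alpha = .05, we will be able to detect a medium effect size", f = .213.
- **Second model for goals of care.** SAP, Goals of Care, describes a logistic GEE (generalised estimating equations) with AR(1) working correlation: "An additive model was conducted with contrast coding for each time point, treatment, and follow-up effects". It prints no coding.
- **Coding.** SAP, Concordance Analysis, repeats that sentence and gives two example rows, both for the sharing visit. Group 1: "Time 2 (1); Time 3 (0), Time 4 (0), Treatment (1), Follow-up (0". Wait-list: "While a participant in the Wait-list (Control) group at time of video sharing would receive contrast coding: Time 2 (0), Time 3 (1", and the row continues with Treatment 1 and Follow-up 0. It adds that "data includes the initial baseline data for both groups and second baseline data for the waitlist group". No 90-day row is shown.
- **Timing.** SAP, Randomization: for Group 1, "videorecording, editing, and viewing will occur within three months of baseline"; for the wait-list, "after the delayed start, their video will be produced and viewed within three months". The length of the delay is not given.

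**The concern.** The hypotheses fix a time point, and the SAP never refers to it. An omnibus interaction asks whether the groups change differently anywhere across the visits. A difference present at sharing and gone by 90 days would satisfy it, and could then be reported as support for H1 or H2.

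For H1 there is a second difficulty. If the additive coding is used, the visit that matters for Group 1 appears to meet a wait-list that has already shared its videos. A Follow-up coefficient near zero could then mean no effect at 90 days or an effect fully kept, depending on a row the reader cannot see. The .90 power could also be carried over to a 90-day claim for which it was not computed.

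**Working it through.** **1. Reproduce the SAP's figure.** Inputs from Power and Sample Size: N = 48, 2 groups, m = 3 visits, correlation r = .5, alpha .05, f = .213.

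Noncentrality = f² × N × m / (1 − r) = 0.045369 × 48 × 3 / 0.5 = 13.07, with 2 and (48 − 2) × 2 = 92 degrees of freedom. Power is .900. The figure is right for its test, which has 2 numerator df.

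**2. What that test responds to.** Let D be the group difference at each visit, in SD units. Then f² = Σ(D − mean D)² / (4 × 3). For (0, d, 0), (0, 0, d) and (0, d, d) the sum of squares is 2d²/3 each time, so f² = d²/18 in all three. At f = .213, d = .213 × √18 = 0.904 SD. Power is .90 whether the difference is at 3 months only, at 6 months only, or at both.

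**3. If time were linear.** With complete, equally spaced continuous data the slope weights are (−0.5, 0, 0.5), so B3 is half the group difference in change from baseline to month 6. Then (0, d, 0) gives B3 = 0, and (0, d, d) gives power 0.88 at 0.904 SD with correlation .5. For self-efficacy this would mainly reflect month 6.

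**4. Is month 6 the 90-day visit, and is the wait-list unexposed then?** Neither is stated. An assumed delay of three months would put wait-list viewing between months 3 and 6; an assumed delay of six months would put it after month 6.

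**5. The additive coding, if it applies to goals of care.** Group 1 has three visits and shares at Time 2, so its 90-day visit is by inference Time 3. The wait-list has its second baseline at Time 2, shares at Time 3 and has its own follow-up at Time 4. Write I and W for the Group 1 and wait-list means, and the number for the time.

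- At Time 2, I2 − W2 = Treatment.
- If the 90-day row is (Treatment 0, Follow-up 1), I3 − W3 = Follow-up − Treatment. The 90-day effect is Follow-up = (I3 − W3) + (I2 − W2), less a baseline adjustment.
- If the row is (Treatment 1, Follow-up 1), I3 − W3 = Follow-up, which is change since sharing and has expectation 0 when the effect lasts. The 90-day effect is Treatment + Follow-up, the same combination of means.

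The design has rank 6 of 6, so the effect is estimable. Wait-list Time 4 gets zero weight. If Group 1's sharing effect differs from the wait-list's by delta, the estimate is off by delta. Labelling Group 1's 90-day visit Time 4 instead gives rank 5 of 6, and the effect is not estimable.

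**6. Illustrative power.** Assumptions: 24 per arm, SD 1, correlation .5, no facility clustering, no loss, two-sided .05. Power ≈ Φ(0.904/SE − 1.96). Each arm contributes the variance of its weighted sum, and SE² = 2 × that variance / 24.

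Example, coded effect, AR(1), no group term, Group 1 weights (−0.75, 1, 1): variance = 0.5625 + 1 + 1 + 2(−0.375 − 0.1875 + 0.5) = 2.4375. SE = √(2 × 2.4375 / 24) = 0.451, and power = Φ(2.006 − 1.96) = 0.52.

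| Contrast | Group term | SE, AR(1) / equal correlation | Power |
|---|---|---|---|
| Coded 90-day effect | no | 0.451 / 0.408 | 0.52 / 0.60 |
| Coded 90-day effect | yes | 0.577 / 0.500 | 0.35 / 0.44 |
| 6-month contrast, wait-list unexposed | no | 0.280 / 0.250 | 0.90 / 0.95 |
| 6-month contrast, wait-list unexposed | yes | 0.354 / 0.289 | 0.72 / 0.88 |

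The fair comparison is between rows with the same group-term setting. The Primary & Secondary Outcomes model includes a group term; the effects listed for the additive model do not.

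**The case against.** Four counter-arguments have weight.

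- **The interaction might isolate the last visit.** The model is printed with a single product term. If time is linear, a difference at sharing only would not make it significant for self-efficacy (step 3). This stands as a condition. But the SAP does not say time is linear, its power figure is for the 2-df test, the linear argument is not exact for a binary outcome, and month 6 is not stated to be the 90-day visit.
- **Follow-up is the 90-day effect.** The additive model has a follow-up term, and the protocol puts the post-sharing survey at 90 days. A reader might infer that the coding makes a 90-day effect inestimable; it does not. An equal sharing effect is a normal assumption of an additive wait-list model. What remains is that the term is tied to no hypothesis, its meaning turns on a row not shown, and the assumption is not stated as a condition of the result.
- **The coding belongs to concordance.** It is printed there only, as examples, for an aim that is descriptive. Its use for H1 is inferred from a shared sentence, and Group 1's place at Time 3 is inferred too. A reader might extend the problem to H2, but no coded model is described for self-efficacy, so the coding cannot affect it.
- **The power statement already names the interaction.** This is correct, and the .90 is not an error. The gap is that no power is given for the comparison the hypotheses make.

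**Conclusion.** The point holds for H1 and H2 in a limited form. The SAP names no test of the 90-day group difference, and the interaction it powers can be significant with no difference at the last visit. This follows from the documents' own figures, given the 2-df test.

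The part about coding is conditional. If the concordance coding governs goals of care and Group 1's 90-day visit is Time 3, the H1 effect depends on an equal sharing effect in both groups and periods, and the only concurrent exposed-versus-unexposed comparison is at Time 2. On the illustrative assumptions, power at 0.904 SD falls from the stated .90 to between 0.35 and 0.60. A 6-month contrast against an unexposed wait-list would have 0.72 to 0.95. These figures are on a continuous scale and ignore clustering within the eight facilities, so for the binary H1 outcome they are indicative only.

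A reader might also conclude that the wait-list has certainly viewed by month 6. The SAP does not support that: it neither states the delay nor maps its Time 3 to the 6-month point.

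**What to change.** 1. For each of H1 and H2, fit time as categorical and make one named, baseline-adjusted 90-day contrast the deciding test in place of the omnibus interaction.
2. If the wait-list has not viewed by month 6, use the 6-month group difference for both hypotheses.
3. Otherwise, for H1, use the 90-day effect from the coded model (Follow-up, or Treatment + Follow-up, according to the row used). Report it as dependent on a constant sharing effect, and identify Time 2 as the only concurrent unexposed comparison. For H2, specify the same model or state that no concurrent unexposed 90-day comparison exists.
4. State that the .90 power is for the interaction, and give power for the named contrast with and without a group term.

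The cost is SAP wording, a small amount of extra analysis and a less favourable power figure. The Goals of Care and Concordance Analysis sections are written in the past tense, so if results have been seen, the contrast should be labelled as added later.
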